1.0 TRIAL SUMMARY

Abbreviated Title	Imaging the flare response from pembrolizumab with FDG PET/CT.
Trial Phase	Correlative
Clinical Indication	Patients with advanced metastatic melanoma who are starting pembrolizumab.
Trial Type	Prospective observational cohort study.
Type of control	No control.
Route of administration	n/a
Trial Blinding	None
Treatment Groups	n/a
Number of trial subjects	30 evaluable subjects
Estimated enrollment period	1 year
Estimated duration of trial	2 years
Duration of Participation	6 months
Estimated average length of treatment per patient	n/a

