2.0 TRIAL DESIGN

2.1 Trial Design

This is a single institution, prospective, observational cohort study of FDG PET/CT as an early measure of response in patients with advanced metastatic melanoma scheduled to start pembrolizumab. Patients may participate in this study if they are greater than 18 years of age; most participants will be receiving care at the clinical practices of the University of Pennsylvania. Patients that may meet eligibility criteria will be approached about study participation regardless of race or ethnic background.

We anticipate enrolling up to 35 participants with metastatic melanoma who meet eligibility requirements for this study. The target accrual goal is to reach 30 evaluable patients, defined as those who complete two (Baseline and 1st Post-therapy) of the three planned FDG PET/CT scans. Thus, accrual is estimated to occur over approximately 1 year.

FDG PET/CT imaging will be used to evaluate glycolytic activity at sites of metastatic disease using the FDA approved clinical Positron Emission Tomography (PET) radiotracer, [¹⁸F]Fluorodeoxyglucose (FDG). Study imaging will be performed in a manner identical to standard clinical FDG PET/CT imaging procedures used at the Hospital of the University of Pennsylvania using a dedicated whole-body PET/CT scanner. For each PET scan static images from the vertex of the skull to toes will be acquired approximately 60 minutes after injection of FDG. Imaging data will be processed as per standard protocol. The study will be performed under the regulatory approval of the Penn Institutional Review Board (IRB).

A total of three FDG PET/CT exams will be performed as follows:

- **Baseline:** A restaging FDG PET/CT will be obtained no more than 4 weeks prior to initiation of pembrolizumab to assess baseline, pre-therapy tumor glycolytic activity. This exam will be obtained for study purposes, although in some cases it may be obtained as clinical standard of care for restaging of disease prior to initiation of a new line of therapy. If this exam is obtained as clinical standard of care, it may occur prior to consent and enrollment in this study.
- **1st Post-therapy:** at approximately 3 weeks (\pm 3 weeks) following the start of pembrolizumab, a post-therapy FDG PET/CT will be obtained. This exam will be obtained for study purposes, to assess glycolytic activity at sites of metastatic disease at an early time-point.

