- **2nd Post-therapy:** When clinically indicated, as per the judgment of the patient's oncologist, a restaging FDG PET/CT will be obtained at > 10 weeks following the start of pembrolizumab. This exam is clinical standard of care for restaging of disease after initiation of a new line of therapy, and would be performed even if the patient was not enrolled in the study. In some cases MRI or CT imaging may be performed as standard of care for restaging disease instead of FDG PET/CT.

[figure not shown]
Almost all of the patients treated for melanoma in the University of Pennsylvania Health System (UPHS) have consented to participate in the Penn Melanoma Tissue Collection Program (UPCC #08607, IRB #703001). For patients participating in this program, blood samples will be collected, processed, and stored according to the program's standard operating procedure. Currently, this includes drawing less than 65 mL of blood according to the following schedule (after initiation of pembrolizumab): weeks 0, 3, 6, 9, 12, 15, and at 1 year. For the purposes of this study, patients will have an additional sample of blood drawn at approximately 1 week after starting pembrolizumab; this sample will also be collected, processed, and stored according to the Penn Melanoma Tissue Collection Program standard operating procedure. If patients have not consented to participate in the Penn Melanoma Tissue Collection Program, then no blood samples will be drawn for the purposes of this study. Analysis of blood samples will include, but is not limited to, analysis of serum cytokines, chemokines, and T cell markers. This data will be correlated to patient response as well as changes in tumor FDG uptake. Some of these studies will be performed upon receipt of additional funding. There may be patients for which some or all of these blood draws are not possible, in this case it will be documented in the CRF and the blood draws may be omitted and it will not be considered a protocol deviation. Experimental pathology results will not be reported to the participant and will have no impact on the treatment decisions made by the treating physician.

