4.1.2 Rationale for Endpoints

4.1.2.1 Primary Endpoint

Objective response to therapy at 6 months, based on imaging and the clinical evaluation of the patient, is an acceptable primary endpoint in this prospective, observational cohort study of FDG PET/CT as an early measure of response in patients with advanced metastatic melanoma. Response will be determined by RECIST version 1.1. While either CT or MRI may be utilized, as per RECIST 1.1, CT is the preferred imaging technique in this study. Patients will be categorized as responders (i.e., complete response or partial response) or nonresponders (stable disease or progressive disease).

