5.2 Subject Recruitment and Screening

Patients will generally be offered enrollment at the time of their office visit to oncology at the Hospital of the University of Pennsylvania. Study personnel or an investigator will present the patient with information regarding the study and enrollment. Enrollment into the study will be presented as optional and will not impact clinical management or choice of therapeutic intervention. It will be emphasized that enrollment in the study is not mandatory and that failure to enroll will not result in prejudice by the treating clinicians and will not affect patient care.

All patients being considered for the study and eligible for screening must sign an informed consent for the study prior to any study specific procedures. Patients will generally have their baseline FDG PET/CT performed as a research scan. Occasionally, the baseline FDG PET/CT may be ordered by a treating physician as part of standard medical care, in which case the scan may occur before the patient is consented and enrolled in this study.

Information from this baseline FDG PET/CT scan will be compared to the post-therapy FDG PET/CT scans. FDG PET/CT scans performed at an institution outside of University of Pennsylvania health system will not be able to be used in this study.

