This is a pilot correlative study of FDG PET/CT imaging to evaluate early response to immunotherapy. We will first begin with a descriptive analysis. For continuous variables, we will generate graphs and descriptive statistics (e.g., means, standard deviations, medians and inter-quartile range). Categorical variables will be described by frequencies, proportions and 95% exact confidence intervals. Change in tumor FDG uptake will be closely examined. It is likely that change in tumor SUVmax >20% will be classified as a FDG “flare” and the number of patients with a flare will be computed.

Next, associations between change in tumor FDG uptake with clinical outcomes will be conducted. Change in tumor FDG uptake at 3 weeks will be compared between responders and nonresponders by a two sample t-test. Also, objective response rates will be compared between patients with or without FDG “flare” by Fisher’s exact test.

PFS and OS will be estimated by the method of Kaplan and Meier. Median values and 95% confidence intervals will be calculated. PFS and OS will be compared between patients with or without FDG “flare” by the log rank test. Cox regression may be used to assess the effect of continuously scaled measurements of FDG change. For all survival analyses, a landmark analysis will be performed. Here, PFS or OS are defined from a landmark, which is 3 weeks after initiation of pembrolizumab. The landmark method is necessary because the change in tumor FDG uptake is known at 3 weeks. Serum and tissue biomarkers will be correlated with change tumor FDG uptake, using Pearson correlation or Spearman’s correlation, as appropriate. Within-patient pre-/post-treatment changes in biomarkers will be evaluated by paired Student’s t-test or Wilcoxon signed ranks test, as appropriate. We will test for an association between post-/pre-treatment fold change in immune biomarkers in serum and tissue and objective response, progression-free survival, and overall survival using logistic regression (for response) and Cox regression (for time-to-event outcomes) using landmark survival analysis.

8.5 Sample Size Justification:

The target is 30 evaluable patients, which may require up to 35 enrolled patients. Based on our clinical experience, we assume a 50% objective response rate, thus there will be 15

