11.0 APPENDICES

11.1 Common Terminology Criteria for Adverse Events V4.0 (CTCAE)

The descriptions and grading scales found in the revised NCI Common Terminology Criteria for Adverse Events (CTCAE) version 4.0 will be utilized for adverse event reporting. (<http://ctep.cancer.gov/reporting/ctc.html>)

11.2 Response Evaluation Criteria in Solid Tumors (RECIST) 1.1 Criteria for Evaluating Response in Solid Tumors

RECIST version 1.1* will be used in this study for assessment of tumor response. While either CT or MRI may be utilized, as per RECIST 1.1, CT is the preferred imaging technique in this study.

* As published in the European Journal of Cancer:

E.A. Eisenhauer, P. Therasse, J. Bogaerts, L.H. Schwartz, D. Sargent, R. Ford, J. Dancey, S. Arbuck, S. Gwyther, M. Mooney, L. Rubinstein, L. Shankar, L. Dodd, R. Kaplan, D. Lacombe, J. Verweij. New response evaluation criteria in solid tumors: Revised RECIST guideline (version 1.1). *Eur J Cancer*. 2009 Jan;45(2):228-47.

In addition, volumetric analysis will be explored by central review for response assessment.

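### Nothing in the plan keeps whoever grades response from knowing the 3-week FDG PET, which is the predictor in the primary test

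*Combined protocol and SAP*

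**What the plan says.** The outcome in primary objective 2 is set in section 4.1.2.1: "Objective response to therapy at 6 months, based on imaging and the clinical evaluation of the patient, is an acceptable primary endpoint". The same section then makes RECIST 1.1 the determining rule and adds "While either CT or MRI may be utilized, as per RECIST 1.1, CT is the preferred imaging technique in this study". Section 8.3 also defines response by RECIST. Neither section names who reads response or what that reader may see. (They also time the assessment differently, at 6 and 3 months. That is a separate matter.)

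The predictor and test are in section 8.4: "Change in tumor FDG uptake at 3 weeks will be compared between responders and nonresponders by a two sample t-test". Section 8.5 makes the test one-sided at 5%.

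On access to the scan, the trial summary gives "Trial Blinding None". The 3-week PET is obtained for study purposes, but section 2.1 says "Study imaging will be performed in a manner identical to standard clinical FDG PET/CT imaging procedures". Under sections 2.1, 4.1.2.3, 6.1 and 7.1.2.3, a marked change in FDG activity may decide which lesion is biopsied, with the biopsy scheduled within 7 days of the scan.

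The plan does contain a non-disclosure rule, repeated in sections 2.1, 4.1.2.3 and 7.1.2.3, but for laboratory work: "Experimental pathology results will not be reported to the participant and will have no impact on the treatment decisions made by the treating physician". No equivalent sentence covers the PET.

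**The concern.** Primary objective 2 asks whether an early FDG change goes with later objective response. That requires response to be graded independently of the FDG change. If the grader knows the 3-week result and a case is borderline, the scan may tip the category, and the t-test then partly measures agreement between the scan and a grade the scan influenced.

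The direction cannot be fixed in advance. A reader who shares the study's flare hypothesis may take a rise as a sign of response. A reader who takes rising uptake as growth may lean toward progression; section 4.1 itself warns that immune infiltration can be mistaken for tumor growth on CT. The first inflates the false-positive rate of the planned one-sided test. The second hides a real association.

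There is a second route. The treating team sets therapy (section 2.2, footnote 1), so a treatment change prompted by the scan could alter the response itself. Masking the response reader does not close that route, so such changes need to be recorded.

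**Working it through.** **1. The plan's own figure.** Inputs from section 8.5: 15 responders, 15 nonresponders, a 1.0 SD difference, one-sided 5%. With df = 28 the critical value is 1.701, and the noncentrality is 1.0 × √(15 × 15 / 30) = √7.5 = 2.739. Exact noncentral-t power is 84.8%, against the stated 84%. The figure reproduces. The issue is bias, not the sample-size arithmetic.

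**2. Assumed inputs.** The documents give no count of borderline cases. I take k = 3, 4 or 6 of 30 as illustrations. FDG change is standard normal and unrelated to true response. Clear cases split evenly; a borderline case is called a responder if its FDG change is above zero.

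**3. Hand check of false positives.** The mean of a standard normal above zero is √(2/π) = 0.798, so the spurious difference between graded groups is about

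Δ = 2 × 0.798 × k/30,

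and the rejection rate is about P(Z > 1.701 − 2.739 Δ).

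- k = 3: Δ = 0.160; 1.701 − 0.437 = 1.264; about 10.3%
- k = 4: Δ = 0.213; 1.701 − 0.583 = 1.118; about 13.2%
- k = 6: Δ = 0.319; 1.701 − 0.874 = 0.827; about 20.4%

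This is rough: with k = 0 it gives 4.4% because a normal tail replaces the t tail.

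**4. Simulation of the same model, one-sided 5% t-test, no true association.**

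| Borderline cases | Rise graded as response, all follow the scan | Half follow the scan | Rise graded as progression |
|---|---|---|---|
| 3 | 10.8% | 7.7% | 1.5% |
| 4 | 12.8% | 8.1% | 0.9% |
| 6 | 19.9% | 10.7% | 0.4% |

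Repeat runs differ by less than one percentage point. With no borderline cases the test holds at about 5%.

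**5. Power when a rise is read as progression.** Here each patient has a chance m of being graded by which side of the midpoint the FDG change falls on, and the true difference is 1.0 SD. With m = 10% (30 × 0.10 = 3 patients on average), power falls from 84.8% to 58% and the mean observed difference from 1.0 to 0.73 SD. With m = 20% (6 patients), power is 29% and the difference 0.46 SD. At m = 30% the difference is still positive, at 0.18 SD.

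**6. How many grades change.** In this second model with no true association, m = 10% changes 5% of grades, or 30 × 0.05 = 1.5 patients. The other scan-led grades agree with the true category by chance. In that setting, with a rise read as response, the false-positive rate is 11.2%.

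**The case against.** The best reply is that the grading rule is already anatomic. Response is determined by RECIST 1.1 on CT or MRI, SUV is not an input, and the study is an openly unblinded observational pilot. This stands in part: it limits how far a grader can drift. It does not remove the problem, because section 4.1.2.1 also names clinical evaluation as a basis and nothing separates the PET from the response read.

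A second reply is that the largest figures are a worst case in one direction. That also stands, which is why the half-following and opposite-direction columns are shown beside them.

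Some stronger readings are tempting, and the documents do not support them.

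- A reader might infer that the 3-week result is given to the treating team or the grader. No section says so. The plan only lacks a rule against it.
- A reader might infer that a central RECIST read is already in place. Section 11.2 says only that "volumetric analysis will be explored by central review for response assessment". That is exploratory volumetry, and it is not stated to be masked.
- A reader might set section 5.2 against the silence on PET. Its wording, "will not impact clinical management or choice of therapeutic intervention", concerns the offer of enrollment, so there is no contradiction to reconcile.
- A reader might conclude that scan-driven treatment changes could reverse the association. Suppose flare is seen in 9/15 responders and 0/15 nonresponders (Fisher p = 0.0007). Moving 2 or 3 flaring responders to nonresponse gives 7/13 vs 2/17 (p = 0.020) or 6/12 vs 3/18 (p = 0.102). The direction is kept, so this is attenuation, and in a secondary test.

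**Conclusion.** The point holds as a missing safeguard. The trial is unblinded, the primary response grade admits clinical judgment beyond RECIST measurements, and nothing prevents the grader from knowing the predictor. The possible effect is material for 30 patients. If three borderline cases follow the scan, the nominal 5% error roughly doubles to about 11%; if six do, it reaches about 20%. If only half of the borderline cases follow the scan, the range is about 8 to 11%. If the bias runs the other way, false positives fall below 5% and power at 1.0 SD could drop to around 58% with about three scan-led grades.

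These sizes rest on assumed counts and on grading by the sign of the FDG change. They show sensitivity and do not predict what will happen. It has not been shown that the scan will be disclosed or that any grade will be influenced by it. The change is worth making because it is cheap and protects primary objective 2.

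**What to change.** In sections 4.1.2.1 and 8.3, state that the RECIST 1.1 category is assigned from CT or MRI measurements (including the CT part of a restaging PET/CT where RECIST 1.1 allows it) by whoever already reads response. The category should be recorded before, and without access to, the 3-week PET, its SUV values or the flare class. Delete the clause that makes the patient's clinical evaluation a basis for grading.

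Add one CRF item: did the treating team see the 3-week PET result, and did treatment change afterwards? Report the count descriptively. This records what happened and directs no clinical decision. An analysis without those patients may be added as a sensitivity analysis only: it selects on an event after the scan that may depend on the predictor, so it cannot recover the undisturbed association.

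The cost is wording, one CRF item and some care in the order or masking of reads. It changes neither the sample size nor the nominal power. The downside is that sections 2.1 and 5.1.2 allow restaging by, and measurable disease seen on, FDG PET/CT, and section 7.1.2.2 describes its CT part as low-dose. A few patients restaged only by PET may therefore be harder to classify; report how many.

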4.1.2.2 Secondary Endpoints

Progression free survival (PFS), is defined as the time from initiation of Pembrolizumab to documented disease progression, death due to any cause or last patient follow-up that documented lack of disease progression.

Overall survival, is defined as start date of Pembrolizumab until death from any cause or last patient contact alive. Survival data will be obtained from the electronic medical records.

4.1.2.3 Biomarker Research

Almost all of the patients treated for melanoma in the University of Pennsylvania Health System (UPHS) have consented to participate in the Penn Melanoma Tissue Collection Program (UPCC #08607, IRB #703001). For patients participating in this program, blood samples will be collected, processed, and stored according to the program's standard operating procedure. Currently, this includes drawing less than 65 mL of blood according to the following schedule (after initiation of pembrolizumab): weeks 0, 3, 6, 9, 12, 15, and at 1 year. For the purposes of this study, patients will have an additional sample of blood drawn at approximately 1 week after starting pembrolizumab; this sample will also be collected, processed, and stored according to the Penn Melanoma Tissue Collection Program standard operating procedure. If patients have not consented to participate in the Penn Melanoma Tissue Collection Program, then no blood samples will be drawn for the purposes of this study. Analysis of blood samples will include, but is not limited to, analysis of serum cytokines, chemokines, and T cell markers. This data will be correlated to patient response as well as changes in tumor FDG uptake. Some of these studies will be performed upon receipt of additional funding. There may be patients for which some or all of these blood draws are not possible, in this case it will be documented in the CRF and the blood draws may be omitted and it will not be considered a protocol deviation. Experimental pathology results will not be reported to the participant and will have no impact on the treatment decisions made by the treating physician.

Patients may undergo tumor biopsy as part of their clinical care prior to initiation of pembrolizumab. For patients participating in the Penn Melanoma Tissue Collection Program, these pre-therapy tissue samples will be collected, processed, and stored according to the program's standard operating procedure. For the purposes of this study, patients will have a post-therapy tumor biopsy which will be scheduled within 7 days after the 1st Post-therapy FDG PET/CT; this tissue will also be collected, processed, and stored according to the Penn Melanoma Tissue Collection Program standard operating procedure. If patients have not consented to participate in the Penn Melanoma Tissue Collection Program, then no tumor biopsies will be performed for the purposes of this study. The biopsy techniques preferred for this study include core biopsies or surgical biopsies. The same biopsy techniques should be used as routinely used for a given tumor lesion/location. When possible, the post-therapy tumor biopsy should target the same lesion that was biopsied pre-therapy; if the original lesion cannot be biopsied, then a lesion with a significant change in FDG activity should be targeted for biopsy. Alternatively, the largest lesion or most accessible lesion may be biopsied. Analysis of tissue samples will include, but is not limited to, analysis of tumor-infiltrating lymphocytes (TILs) and macrophages. This data will be correlated to patient response as well as changes in tumor FDG uptake. Some of these studies will be performed upon receipt of additional funding. There may be patients for which a pre- or post- therapy tumor biopsy is not performed; those cases will be documented in the CRF and will not be considered a protocol deviation. In some cases tissue may be collected outside of the 7 day window following the 1st Post-therapy FDG PET/CT; this will not be considered a protocol deviation. Experimental pathology results will not be reported to the participant and will have no impact on the treatment decisions made by the treating physician.

For patients participating in the Penn Melanoma Tissue Collection Program, we will follow the standard operating procedure regarding archival tissue access for patients undergoing a biopsy or surgery on melanoma or other skin cancer for diagnosing, treating or research purposes, but for which there is no applicable left over fresh tissue, or patients who had a biopsy or surgical procedure done on melanoma or other skin cancer for diagnosing, treating or research purposes at the University of Pennsylvania Health System (UPHS) or at an institution outside of UPHS. If patients have not consented to participate in the Penn Melanoma Tissue Collection Program, then no archival tissue will be requested.

